2.3.8 Definitions

Chronic hypertension will be defined according to ACOG guidelines as blood pressure measurement of EITHER ≥ 140 mm Hg OR diastolic ≥ 90 mm Hg on at least 2 occasions, at least 4 hours apart, prior to 20 weeks gestation ¹

Hypertensive disorders of pregnancy will be defined according to ACOG guidelines.¹ The minimum criteria for a diagnosis of HDP are as follows:

- Blood pressure measurement of EITHER systolic ≥ 140 mm Hg OR diastolic ≥ 90 mm Hg on at least 2 occasions, at least 4 hours apart, between 20 weeks gestation and delivery
- Blood pressure measurement of EITHER systolic ≥ 160 mm Hg OR diastolic ≥ 110 mm Hg on at least 2 occasions qualifies as severe features

The following investigations are routinely undertaken in the clinical setting once HDP is identified in order to further categorize HDP into more specific diagnoses. These results will be reviewed for each patient to ensure the correct diagnosis has been assigned to the patient. Blood pressure findings as above with none of the findings listed in the table below satisfies a diagnosis of gestational hypertension.

Type of test	Cutoffs	Diagnosis
Urine	-24-hour protein concentration > 300 mg OR -Protein/Creatinine ratio > 0.3	Preeclampsia
Serum	-Platelets <100,000/microliter OR -Creatinine >1.1 mg/dL, or doubling from baseline OR -LFTs > twice the upper limit of normal concentration or twice baseline	Preeclampsia with severe features
Signs/symptoms: any of the following, if not accounted for by another diagnosis	-New-onset, refractory cerebral or visual disturbances -Severe persistent right upper quadrant or epigastric pain unresponsive to medication -Pulmonary edema -Blood pressure ≥ 160 systolic OR ≥ 110 diastolic	Preeclampsia with severe features
Serum	-Platelets <100,000/microliter AND -Evidence of hemolysis	Hemolysis, elevated liver enzymes and low platelet count (HELLP) syndrome

	AND -LFTs > twice the upper limit of normal concentration or twice baseline	
Signs/symptoms	New-onset, grand mal seizure, with no history of seizure disorder and not accounted for by any other diagnosis	Eclampsia

2.4 Statistical Analyses

2.4.1 Sample size and statistical power

Though data on the rate of follow up in patients with HDP are scarce, we will presume that the percentage of patients who record their blood pressures accurately postpartum is similar to the rate noted in the few studies that have measured similar metrics, approximately 43.7%.¹⁵ We currently have IRB approval for a retrospective study to assess the postpartum follow up of women with HDP over the past 2 years at CUIMC (protocol AAAR9887). Until data collection for this study is complete, we will not precisely know the baseline rate of compliance with blood pressure measurements in the first 7-10 days postpartum. Therefore, in order to err on the side of making sure we are well powered, we will use 60% as an estimated percentage of twice daily blood pressures that are recorded in the usual care group. Aiming to achieve a rate of 80% for twice daily blood pressure recordings in the study group with 80% power, we would need to recruit 81 patients to each group. Allowing for the possibility of loss to follow-up and to compensate for the reduced power due to statistical adjustment for potential confounders, we inflated the sample size by 25%. 101 patients will therefore need to be recruited to each group, or 202 patients total. The randomization sequence was built based on an overestimate of dropout rate. Therefore, we increased our target enrollment from 202 to 220. Once the sample size is reached, enrollment will stop.

2.4.2 Statistical analysis

For analysis of discrete (categorical) data in independent samples, the Chi-squared test or Fisher exact probability test will be utilized. For group comparisons, continuous data that satisfy the assumptions of normality and homoscedasticity (homogeneity of variance) will be analyzed by t-test (for 2 independent samples) or analysis of variance (>2 groups, ANOVA) with post hoc comparisons by Scheffe tests. When possible, continuous data that do not fulfill the aforementioned assumptions will be mathematically transformed (e.g., logarithmic transformation) before performing t-tests or ANOVA. In some cases, data that do not satisfy these assumptions will be analyzed by nonparametric methods [Mann-Whitney U Test (for two independent samples) or Kruskal-Wallis One-Way ANOVA (for more than two independent

samples)]. Significant Kruskal-Wallis ANOVAs will be followed by Dunn tests for post hoc analysis. The degree of linear association between variables will be measured by the Pearson product moment correlation coefficient or the Spearman rank-order correlation coefficient and their corresponding tests of significance. Multivariate linear or logistic regression will be utilized where appropriate. In all cases, statistical significance will be assumed when $p < 0.05$. Propensity score analysis will be used as a balancing score as deemed necessary.

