2.3.4 Recruitment, Screening and Enrollment

We will use a recruitment strategy designed and utilized by the OB department. An OB research coordinator (RC) will perform daily chart screen of all women admitted to the CUIMC postpartum unit (CHONY 5 central, 6 central and 10 central). Permission from healthcare providers will be obtained prior to the OB RC contacting participants. Eligible women will then be recruited from the aforementioned postpartum units. After obtaining written informed

consent, participants’ sociodemographic characteristics will be collected. Information regarding their diagnosis of HDP and delivery information will be collected at that time as well. They will then be randomized to either usual care, as defined above, or the study group. Randomization will occur in REDCap. Those in the study group will be educated on use of the Philips equipment by research personnel who will have been educated on use of the equipment, with support over the phone by a Philips representative. Nursing staff will be familiarized with the equipment as well, and will be available to answer any questions the patient might have. Patients in the study group will be provided with the Philips telehealth kit, complimentary of participating in the study, prior to being discharged from the hospital (see “Equipment and Software” section, below). Their chart will be created in the eCC prior to discharge from the hospital by the RC.

Once home, the patient will receive a “Welcome Call” from a Philips representative, which will ensure that the equipment is set up properly and that all the patient’s questions are answered. If the patient has any remaining difficulty with equipment, Philips will arrange for a home visit from a representative, which will occur within 72 hours. Prior to that visit, if the Bluetooth system is not working properly, the cuff will still work as a normal blood pressure cuff, so the patient will be able to take measurements.

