2.3.6 Outcomes

- 1) **Primary outcome:** Our primary outcome will be percentage of the recommended twice daily blood pressures reported between hospital discharge and outpatient blood pressure assessment.
- 2) **Secondary outcomes:** Secondary outcomes will include:
 1. Percentage of recorded blood pressure values during that time frame that are elevated (>140 systolic OR >90 diastolic)
 2. Percentage of elevated blood pressures that triggered a phone call to an obstetric provider
 3. Rate of attendance at outpatient blood pressure assessment
 4. Incidence of elevated blood pressure at the outpatient blood pressure assessment
 5. Rate of outpatient assessment for postpartum care
 6. Incidence of elevated blood pressure at the postpartum assessment
 7. Time to initiation of antihypertensive medications (in patients who were not on medications at time of discharge) and adjustment of antihypertensive medications
 8. Final dosage of antihypertensive medications at 6 weeks postpartum
 9. Readmission rate
 10. Rate of emergency department visits
 11. Rate of HDP-associated morbidities (e.g.: stroke, seizure, PRES)
 12. Percentage of patients who require a referral to primary care physicians after being discharged from obstetric care at the postpartum visit
 13. Patient satisfaction with the method, to be assessed via a validated clinical survey (attached separately in the document entitled “Surveys”).

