2.5. Anticipated outcomes

The primary outcome will be the difference in the percentage of twice-daily blood pressures reported between hospital discharge and the outpatient blood pressure assessment. We anticipate that the patients enrolled to RPM will have a significantly higher percentage of blood pressures recorded. Thus, there will be more data, available at an earlier time point in the postpartum period, which providers can use to make decisions regarding titrating medications and need for closer monitoring. We anticipate that patients enrolled in RPM will have more communication with their obstetric providers, higher compliance with their scheduled postpartum visits, and better blood pressure control at 6 weeks postpartum. We also anticipate that these patients will feel like they have had a more active role in their own care, and will feel more connected to their providers during the fragile and currently under-monitored postpartum period.

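### Section 2.4.2 names no primary analysis for the percentage of readings reported, and its transformed, rank and logistic branches do not estimate the difference the plan calls primary

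*Combined protocol and SAP*

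**What the plan says.** **Outcome.** Section 2.3.6: "Our primary outcome will be percentage of the recommended twice daily blood pressures reported between hospital discharge and outpatient blood pressure assessment". Section 2.5 turns this into a contrast: "The primary outcome will be the difference in the percentage of twice-daily blood pressures reported between hospital discharge", with the window closing at the outpatient assessment. Neither section says whether the percentage is computed for each woman.

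**Analysis.** Section 2.4.2 is the whole analysis text and does not mention the primary outcome. It assigns chi-squared or Fisher tests to categorical data and the t-test to continuous data that are normal with equal variances. Otherwise: "When possible, continuous data that do not fulfill the aforementioned assumptions will be mathematically transformed (e.g., logarithmic transformation"; then "In some cases, data that do not satisfy these assumptions will be analyzed by nonparametric methods". It adds "Multivariate linear or logistic regression will be utilized where appropriate" and "Propensity score analysis will be used as a balancing score as deemed necessary". It names no covariates, effect estimate or confidence interval.

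**Sample size.** Section 2.4.1 sets 60% against 80%, 80% power and 81 per group. It inflates by 25% for loss to follow-up and "to compensate for the reduced power due to statistical adjustment for potential confounders", giving 101 per group; the target was later raised to 220 in total.

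**Data before randomisation.** Section 2.3.4 collects sociodemographic characteristics after consent, and continues: "Information regarding their diagnosis of HDP and delivery information will be collected at that time as well. They will then be randomized".

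**The concern.** The t-test has a stated trigger. Once it fails, the choice between transformation and ranks is left to judgement, and so is the use of regression or propensity scores at any stage.

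For this outcome the trigger may well fail, because a percentage is bounded at 0 and 100. It may also contain zeros. Control logs are collected at the 7-10 day visit (section 2.3.1), and section 2.1 presumes that only about half of patients attend it. Whether a woman who misses that visit counts as 0% or as missing is not stated.

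The branches then answer different questions. A log analysis compares geometric means and is undefined at 0%. Mann-Whitney compares orderings. Logistic regression gives an odds ratio. None of these is a difference in percentage points. At stake is whether the reported test addresses the declared quantity, and whether that was settled before the data were seen.

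**Working it through.** **1. The plan's own figure.** Inputs from section 2.4.1: 0.60 and 0.80, power 80%. Two-sided 5% is assumed, since 2.4.2 gives p < 0.05 without sidedness. With a pooled proportion of 0.70:

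n = [1.96·√(2·0.70·0.30) + 0.8416·√(0.24 + 0.16)]² / 0.20² = 81.2 per group, against 81 stated. Then 81 × 1.25 = 101.25, stated as 101.

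So the size was computed as if each woman were a yes/no. Section 2.4.1 also begins with a percentage of patients (43.7%) and then switches to a percentage of readings (60%).

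**2. Is that size enough for a per-woman percentage?** The documents give no SD. The largest SDs possible at means of 60 and 80 are 49.0 and 40.0 (every woman at 0 or 100). Their root mean square is √[(2400 + 1600)/2] = 44.7. Then n = 2·(1.96 + 0.8416)²·2000/20² = 78.5 per group. A linear analysis of the percentage therefore needs no larger sample.

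**3. What the rank branch does.** Assumed control shape: 35% at 0%, the rest normal with mean 92 and SD 6, so the mean is 0.65 × 92 = 59.8. There are 110 women per arm and values are capped at 100. The chance that a monitored (RPM) woman exceeds a control, counting ties as half, follows by hand, ignoring the cap:

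- RPM normal(80, 12): 0.35 + 0.65·Φ(−12/√180) = 0.35 + 0.65 × 0.186 = 0.47
- RPM 10% at 0%, rest normal(89, 8): 0.9·0.35 + ½·0.1·0.35 + 0.9·0.65·Φ(−3/10) = 0.56
- RPM normal(70, 12): 0.35 + 0.65·Φ(−22/√180) = 0.38

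| RPM shape | Mean difference | Means favour RPM | Mann-Whitney favours RPM | Mann-Whitney favours usual care |
|---|---|---|---|---|
| normal(80, 12) | 20.2 | about 99.9% | about 0.5% | about 13% |
| 10% at 0, rest normal(89, 8) | 20.3 | about 98% | about 28% | under 0.1% |
| normal(70, 12) | 10.2 | about 65% | essentially none | 80-82% |

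The last three columns are percentages of simulated trials significant at 5%; repeat runs differ by a point or two.

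Milder shapes do much less harm. At 81 per group and means of 60 and 80, with 30% and 10% at zero, the t-test, log(y+1) and Mann-Whitney have power 94%, 92% and 88%. With almost no zeros all three are near 100%.

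**4. What the log branch does.** Assume nearly equal means: 15% of controls at 0% and the rest normal(78, 15), against RPM normal(66, 18). Welch's t rejects in 5% of trials. Log(y+0.5), log(y+1) and log(y+10) reject in 96%, 93% and 56%. The added constant drives the answer.

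**5. What adjustment costs or gains.** Variance ratio, adjusted to unadjusted = (1 − R²)(n − 3)/(n − k − 3), with n = 220. Five illustrative covariates (insurance, education, HDP diagnosis, any prior pregnancy, home language) use k = 1 + 2 + 2 + 1 + 1 = 7 parameters. A missing category for each makes k = 12.

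- Useless covariates: 217/210 = 1.033, standard error +1.7%; with k = 12, 217/205 = 1.059, +2.9%.
- Break-even R² = k/(n − 3): 7/217 = 0.03; 12/217 = 0.055.
- k = 7 and assumed R² of 0.10, 0.20, 0.30: standard error −3.6%, −9.1%, −15.0%.
- Power at 20 points with R² 0.20: 99.1% to 99.8% at an assumed SD of 34; 91.0% to 95.3% at SD 44.7.

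**6. Choosing between analyses.** If the smaller p of the unadjusted and adjusted tests were reported, simulated null rejection at n = 220 would be 6.3%, 6.9% and 7.5% for R² 0.10, 0.20 and 0.30. Each method used alone stays near 5%.

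**The case against.** **The rules are not empty.** Section 2.4.2 does choose by data type and assumption check. If the outcome were a yes/no per woman, it would name chi-squared or Fisher. This stands in part: the unit must be settled first. For a percentage, the discretion remains.

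**The reversal needs a special shape.** A reader might infer that the plan would report the wrong direction. The 80-82% figure needs RPM women to report less (70%) than those controls who report at all (92%), with no RPM woman at zero. At the planned RPM mean of 80% it falls to about 13%, or under 0.1%. The documents do not support a general claim of reversal. The loss of power in those two cases remains.

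**The zeros depend on an unstated rule.** Women who miss the visit count as 0% only if the plan says so. This stands, and the result is conditional on it.

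**The log figures are not the plan's error rate.** The log is given only as an example of a transformation. In step 4, log(y+1) itself failed a normality test in all 2,000 simulated trials, so a careful analyst would not rely on it. What stands is that it targets a different quantity.

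**The 6% to 8% error is hypothetical.** A reader might infer that the plan's type I error is inflated. The plan does not say that the better of two results will be reported; it only leaves that possible.

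**Adjustment is optional.** An unadjusted mean difference with robust errors estimates the same quantity, and nothing in the documents shows that the proposed covariates predict reporting. This stands. Adjustment is recommended because section 2.4.1 already expects it and leaving it open creates a choice. It is not the only valid analysis.

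**Conclusion.** The point holds. No primary analysis is named, the unit of the outcome is unclear, and three branches open to the analyst (transformed, rank, logistic) do not estimate the declared difference. The sample size is not in question here: 81 per group covers a 20-point mean difference at SD 44.7, before any loss to follow-up.

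The size of the problem is conditional. With many control zeros (35% assumed) and a true 20-point benefit, Mann-Whitney favours the monitored arm in only about 0.5% to 28% of trials, where a comparison of means succeeds in 98% or more. With few zeros the methods agree on significance, though they still report different quantities. All shapes, SDs and R² values are assumptions. The gain from adjustment cannot be known from the documents and is small in power terms at the planned effect. The documents do not support reading this as a predicted reversal, as an error rate above 5%, or as proof that adjustment is required.

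**What to change.** In sections 2.3.6 and 2.5, define the outcome as each woman's percentage: readings reported divided by readings due, not a yes/no.

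In section 2.4.2, name one primary analysis before data are seen:

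- Linear regression of the untransformed percentage on assigned arm, with heteroscedasticity-robust standard errors and no normality pretest, reporting the mean difference in points with its 95% CI.
- Adjustment for a short fixed list recorded before randomisation, for example insurance, education and HDP diagnosis, with a stated rule for missing values. Do not use values updated at discharge; section 2.3.7 has the HDP diagnosis verified then.
- The unadjusted difference as support; rank, transformed and propensity analyses as sensitivity only.

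In section 2.4.1, reword the adjustment remark: in a linear model of a randomised comparison, adjustment does not generally reduce power. Leave the sample size and the 25% inflation as they are.

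Cost: wording, and a few degrees of freedom (standard error up 1.7% with 7 parameters, 2.9% with 12, if the covariates explain nothing). This does not solve control readings lost because the log visit is missed; those need their own rule.

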2.2 Specific aims

Our objective is to trial RPM in the postpartum hypertensive population in a randomized control design, with an aim to increase the number of blood pressure measurements taken during the fragile and under-monitored postpartum period and to thereby improve postpartum blood pressure control and reduce severe morbidity and mortality.

Specific Aim 1. To compare the number of blood pressures recorded in the first 10 days postpartum between patients who have been enrolled in an RPM trial to those who are being treated with the usual care. We hypothesize that women using RPM will have more blood pressure values recorded at outpatient blood pressure assessment compared with patients using the usual care.

- **Sub-aim 1: To compare the percentage of elevated blood pressures that are discussed with an obstetric care provider between patients who have been enrolled in an RPM trial to those who are being treated with the usual care.** We hypothesize that women using RPM will communicate more frequently with their providers regarding elevated blood pressure values.
- **Sub-aim 2: To examine the effect of RPM on blood pressure control at 6 weeks in women with HDP.** We hypothesize that more women using RPM will be normotensive, defined as blood pressure < 140/90 mm Hg, at the end of the postpartum period, compared to those randomized to usual care.

Sub-aim 3: To compare time to outpatient initiation or adjustment of antihypertensive medications in women using RPM compared to the usual care. We hypothesize that women using RPM will have shorter time to initiation of medications or shorter time to change in medication regimen in the outpatient setting than those using the usual care.

Specific Aim 2. To compare rates of compliance with follow up visits between patients who have been enrolled in an RPM trial to those who are being treated with the usual care. We hypothesize that women using RPM will have a higher rate of compliance with outpatient blood pressure assessments and postpartum visits than patients using the usual care

- **Sub-aim 1: To analyze factors associated with poor postpartum follow up in both the study group and the control group.** We hypothesize that factors such as socioeconomic status, wait times at the office or clinic where care is provided, number of children at home, and educational level will be associated with lower follow-up rates.

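### The plan calls p<0.05 significant for every test, with no control of error across 13 secondary outcomes; significance should be reserved for the primary outcome.

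*Combined protocol and SAP*

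**What the plan says.** The combined protocol and SAP, section 2.3.6, names one primary outcome: "Our primary outcome will be percentage of the recommended twice daily blood pressures reported between hospital discharge and outpatient blood pressure assessment". The same section then begins a numbered list with "Secondary outcomes will include" and runs to item 13, "Patient satisfaction with the method, to be assessed via a validated clinical survey". Item 7 names two endpoints: "Time to initiation of antihypertensive medications (in patients who were not on medications at time of discharge) and adjustment of antihypertensive medications".

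Section 2.4.1 sizes the trial on the recording percentage alone, 60% under usual care against 80% in the study group. Section 2.4.2 lists generic tests and sets a single threshold for all of them: "In all cases, statistical significance will be assumed when" p is below 0.05. It does not say whether tests are one- or two-sided.

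The only multiple-comparison procedures named are Scheffe ("with post hoc comparisons by Scheffe tests") and Dunn tests. Both are for comparisons among more than two groups. Neither acts across outcomes in a two-arm trial. The documents give no testing order, allocation of alpha or adjustment across outcomes, and they do not label the secondary outcomes exploratory or descriptive.

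**The concern.** The outcomes that matter most clinically are all secondary: blood pressure control, time to treatment, attendance, readmission, emergency visits and morbidity. The plan expects to learn from them. The abstract makes control and morbidity an overarching goal. Sections 2.2 and 2.5 attach directional expectations to communication, control at 6 weeks, time to medication change, attendance and satisfaction.

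Under a rule that treats every p<0.05 alike, one chance finding among 13 would carry the same formal status as the one comparison the trial was sized for. What is at stake is the reliability of those secondary claims. The test of the primary outcome is not affected.

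**Working it through.** **Inputs.** The threshold of 0.05 for every test is from 2.4.2. The 13 numbered secondary outcomes are from 2.3.6. The rates of 60% and 80%, 80% power, 81 per group and the target of 220 are from 2.4.1. Assumptions: one test per numbered item, two-sided tests, and no true effect on any secondary outcome.

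**1. The plan's own figure.** With a pooled variance under the null and two-sided alpha of 0.05, n per group = [1.96·√(2·0.7·0.3) + 0.8416·√(0.6·0.4 + 0.8·0.2)]² / 0.2² = 81.2. This agrees with the stated 81; power at 81 is 79.9%. A one-sided test would need only 64. The plan's figure therefore supports reading 0.05 as two-sided, and it concerns the primary outcome only. The documents state no family-wise error rate to reproduce.

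**2. Any false positive, independent tests.** The expected number is 13 × 0.05 = 0.65. The chance of at least one is 1 − 0.95^13 = 0.487.

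**3. A false positive favouring RPM, independent tests.** Each two-sided test puts 0.025 in that direction: 1 − 0.975^13 = 0.280.

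**4. Correlated tests.** The documents give no correlations, so a range is shown. With a common correlation ρ between normal test statistics X_i = √ρ·G + √(1−ρ)·E_i, the chance that at least one crosses 1.96 is:

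| ρ | Either direction | Favouring RPM |
|---|---|---|
| 0 | 49% | 28% |
| 0.3 | 42% | 21% |
| 0.5 | 33% | 17% |
| 0.7 | 24% | 12% |

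The last column takes all outcomes as coded so that a positive statistic favours RPM.

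**5. Sensitivity to the count.**

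- Splitting item 7 into initiation and adjustment gives 14 tests: 1 − 0.95^14 = 51%.
- Item 11 (morbidity) is likely to be rare, and 2.4.2 allows Fisher's exact test. With 220/2 = 110 per arm, the test's true size is about 0.0006, 0.006 and 0.023 at assumed event rates of 1%, 2% and 5%. The documents give no rate for this outcome. Dropping it leaves 12 tests: 1 − 0.95^12 = 46%.
- Item 2 (elevated readings that led to a provider call) is unlikely to be null. Under 2.3.1, call-centre nurses in the study arm phone the provider about high-flagged readings if the patient has not. Dropping it as well leaves 11 tests: 1 − 0.95^11 = 43%, and 1 − 0.975^11 = 24% favouring RPM.

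**6. Reference point.** Bonferroni over 13 tests would set 0.05/13 = 0.0038 per test. It is shown for scale and is not recommended here.

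**The case against.** The strongest reply is that secondary outcomes are customarily tested without adjustment, and that this plan already marks its primary outcome. Sections 2.3.6, 2.4.1 and 2.5 all single out the recording percentage. A reader might infer that nothing separates the powered test from the rest, but those sections show otherwise. What is missing is narrower: a statement of how secondary p-values are to be read. The sentence in 2.4.2 points the wrong way on that.

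A reader might also take 49% as the expected error rate. It is the value for independent tests, one per item, and it counts results in both directions. Related outcomes, such as attendance at two visits or elevated pressure at successive times, pull it down, as does rare morbidity. It is not an absolute ceiling either, since splitting item 7 raises it.

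Two further readings go too far. Item 11 is one morbidity rate with examples in brackets, so stroke, seizure and PRES are not three listed outcomes. And the documents do not say that an isolated secondary p<0.05 would be reported as an established effect of RPM. They set a threshold for significance and leave the interpretation open.

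Finally, confidence intervals alone do not remove the problem: 13 independent unadjusted 95% intervals have the same 49% chance that at least one excludes the null. That objection stands, so the intervals must be labelled as unadjusted.

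**Conclusion.** The concern holds for the secondary outcomes and is modest in weight. Applied as written, the rule in 2.4.2 gives a chance of at least one false secondary finding that is several times 5%: 49% under independence and still 24% at a correlation of 0.7. For findings that wrongly favour RPM the range is 28% down to 12%. These figures assume no effect on any secondary outcome, one two-sided test per item, and exact 5% size. Allowing for rare morbidity lowers them a little.

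The primary comparison keeps its 5% error rate, so the trial's main conclusion is not in question. The change is worth making because it is cheap and because the plan shows neither power nor error control for the outcomes concerned.

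**What to change.** Replace the significance sentence in 2.4.2 with:

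> Two-sided p<0.05 defines statistical significance for the primary outcome only. Secondary outcomes and the follow-up-factor analyses are reported as effect estimates with 95% confidence intervals that are not adjusted for multiplicity; any p-values are nominal, and these results are interpreted as supportive or hypothesis-generating.

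This also settles sidedness and covers the analysis of factors linked to poor follow-up (Aim 2, Sub-aim 1). It changes no data collection, sample size or patient care.

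The cost is that the sponsor gives up confirmatory significance claims on individual secondary outcomes, including the hypotheses in Aim 2 and the Aim 1 sub-aims. If any of those must stay confirmatory, the plan would need to name them and set a testing order or adjusted threshold for them before the data are analysed.
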